3.8. Analysis Windows

3.8.1. Definition of Study Day 1 and Other Definitions

Study Day 1 is defined as the day when the first dose of blinded study drug was taken, as recorded on the Study Drug Administration eCRF.

Open-Label Study Day 1 is defined as the day when the first dose of the open-label study drug was taken, as recorded on the Study Drug Administration eCRF.

Study days are calculated relative to Study Day 1. For events that occurred on or after Study Day 1 date, study days are calculated as (visit date – Study Day 1 + 1). For events that occurred prior to Study Day 1, study days are calculated as (visit date – Study Day 1).

Open-Label Study days are calculated relative to Open-Label Study Day 1. For events that occurred on or after Open-Label Study Day 1, study days are calculated as (visit date – Open-Label Study Day 1 + 1).

Follow-up days are for visits occurred during treatment-free follow-up period and calculated as (visit date – last dose date).

Last Dose Date of Blinded Study Drug is the latest non-missing end date of blinded study drug, recorded on the Study Drug Administration eCRF form with “Study Drug Permanently Discontinued” box checked for subjects who prematurely discontinued blinded study drug or who completed blinded study drug according to the Blinded Study Drug Completion eCRF. If the last dose date of blinded study drug is missing (eg, due to lost to follow up) for subjects who prematurely discontinued blinded study drug, or for subjects who are still on blinded study drug, the latest of nonmissing blinded study drug start dates and end dates, the clinical visit dates, and the laboratory visit dates, excluding the dates during open-label treatment and 24-week treatment free follow up, will be used to impute the last dose date of blinded study drug.

For subjects who prematurely discontinued blinded study drug or who completed blinded study drug but did not enter the open-label phase, the **Last Dose Date** is the same as Last Dose Date of Blinded Study Drug.

For subjects who completed blinded study drug and entered the open-label phase, the **Last Dose Date** is the latest non-missing end date of open-label study drug, recorded on the Study Drug Administration eCRF form with “Study Drug Permanently Discontinued” box checked for subjects who prematurely discontinued open-label study drug or who completed open-label study drug according to Open-Label Study Drug Completion eCRF. If the last dose date is missing (eg, due to lost to follow up) for subjects who prematurely discontinued open-label study drug, or for subjects who are still on open-label study drug, the latest of nonmissing open-label study drug start dates and end dates, the clinical visit dates, and the laboratory visit dates, excluding the dates during 24-week treatment-free follow-up, will be used to impute the last dose date.

Last Study Date is the latest of nonmissing study drug (blinded or open-label) start dates and end dates, the clinical visit dates, and the laboratory visit dates, including the 24-week treatment-free follow-up visit date, for subjects who prematurely discontinued study or who completed study according to Study Completion eCRF.

Baseline value for the double-blind phase is defined as the last nonmissing value obtained on or prior to Study Day 1.

Baseline value for the open-label phase is defined as the last nonmissing value obtained on or prior to Open-label Study Day 1.

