During the blinded portion of the study, HBV DNA results will not be distributed to investigators, subjects, or clinical research personnel involved in the clinical conduct of the study. The only exception will be in the event where Grade 4 ALT is maintained for 16 weeks and in the case of ALT flare, both considered situations of medical need, when serial HBV DNA values from Screening through time of event will be made available to the investigator. Additionally, Gilead Drug Safety and Public Health will be provided with unblinding information upon request for expedited reporting of Suspected Unexpected Serious Adverse Reactions (SUSARs).

In the event of a medical emergency where unblinding is required for treating the subject, the investigator may unblind via the IXRS. Gilead recommends but does not require that the investigator contact the Gilead Sciences medical monitor before unblinding in such instances. Treatment assignment should remain blinded unless that knowledge is necessary to determine emergency medical care for the subject. The rationale for unblinding must be clearly explained in source documentation and on the electronic case report form (eCRF), along with the date on which the code was broken. Additionally, the investigator is requested to inform the Gilead medical monitor within 24 hours of obtaining the treatment code.

Blinding of study treatment is critical to the integrity of this clinical trial and therefore, if a subject's treatment assignment is disclosed to the investigator, the subject will have study treatment discontinued. The subject can be offered open-label tenofovir DF after discussion with the Gilead Medical Monitor. All subjects will be followed until study completion unless consent to do so is specifically withdrawn by the subject.

Gilead Drug Safety and Public Health (DSPH) may independently unblind cases for expedited reporting of suspected unexpected serious adverse reactions (SUSARs).

5.2. Description and Handling of Study Drugs – Tenofovir DF Tablet/Oral Powder and Matching Placebos

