3.8.2. Analysis Windows

Subject visits might not occur on protocol specified days. Therefore, for the purpose of analysis, observations will be assigned to analysis windows.

The following windows ([Table 3-2](#) to [Table 3-4](#)) apply to baseline and on-treatment assessments only; ie, data collected during the double-blind phase and open-label phase. For summaries and analyses, assessments will first be categorized into on-treatment assessments occurring during the double-blind or open-label phase, before applying analysis windows.

For subjects who completed blinded study drug and entered the open-label phase, laboratory and DXA assessments that occurred during the period from the first dose date of blinded study drug up to and including the minimum of the Last Dose Date of Blinded Study Drug + 3 days and the Open-label Study Day 1, will be considered as on-treatment during the double-blind phase. If a subject prematurely discontinued blinded study drug or did not enter open-label phase after completion of blinded study drug, then on-treatment assessments during the double-blind phase will be defined as assessments that occurred during the period from the first dose date of blinded study drug to the Last Dose Date + 3 days.

For subjects who entered the open-label phase, on-treatment assessments during the open-label phase will be defined as assessments that occurred during the period from Open-label Study Day 1 up to the Last Dose Date + 3 days.

Off-treatment assessments during the treatment free follow-up (TFFU) phase will be defined as assessments that occurred during the period after the Last Dose Date + 3 days up to the Last Study Date. Assessments during this period are considered post-treatment.

The analysis windows for HBV DNA, hematology, serum chemistry and liver tests, urinalysis, urine pregnancy test, height, weight, and vital sign assessments are presented in [Table 3-2](#).

Table 3-2. Analysis Windows for HBV DNA, Hematology, Serum Chemistry and Liver Tests, Urinalysis, Urine Pregnancy Test, Height, Weight, and Vital Sign Assessments

Visit ID	Nominal Day	Lower Limit	Upper Limit
Baseline			1
Week 4	28	2	41
Week 8	56	42	83
Week 16	112	84	139
Week 24	168	140	195
Week 32	224	196	251
Week 40	280	252	307
Week 48	336	308	363
Week 56	392	364	419
Week 64	448	420	475
Week 72	504	476	531
Week 80	560	532	587
Week 88	616	588	643
Week 96	672	644	713
Week 108	756	714	797
Week 120	840	798	881
Week 132	924	882	965
Week 144	1008	966	1049

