4.2. Disposition of Subjects

The summary of subject disposition will be provided by treatment group and overall. This summary will include the number of subjects screened, subjects not randomized, screen failure subjects who were not randomized, subjects who met all eligibility criteria and were not randomized with reasons for subjects not randomized, subjects in the Randomized Analysis Set, subjects randomized and not treated, and subjects in the Safety Analysis Set.

In addition, the number and percentage of the subjects in the following categories will be summarized using the Safety Analysis Set:

Double-Blind Phase

- Completed double-blind study drug
 - Completed double-blind study drug at Week 72
 - Completed double-blind study drug at Week 48
- Premature discontinuation of double-blind study drug (with summary of reasons for discontinuation of double-blind study drug)

Open-Label Phase

- Entered open-label phase at Week 72
- Entered open-label phase at Week 48
- Continuing open-label study drug
 - Entered open-label extension
- Completed open-label study drug
- Premature discontinuation of open-label study drug (with summary of reasons for discontinuation of open-label study drug)

TFFU Phase

- Entered the 24-week treatment-free follow-up period
- Completed the 24-week treatment-free follow-up period
- Entered the 24-week treatment-free follow-up period, but discontinued due to starting another HBV therapy

Study Completion

- Continuing study
- Completed protocol-planned duration of study
- Premature discontinuation of study (with summary of reasons for premature discontinuation of study)

No inferential statistics will be generated. A flowchart will be provided to depict the disposition. Also, the following by-subject listings will be provided by subject identification (ID) number in ascending order to support the above summary tables:

- Subject disposition including reasons for premature study drug or study discontinuation
- Screen failed subjects with reasons for screen failure

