7.2.3. ALT Flare and Exacerbation of Hepatitis

Summaries of the incidence of ALT flare and exacerbation of hepatitis will be provided by treatment group using the subjects in the Safety Analysis Set for on-treatment occurrences during the double-blind phase and off-treatment occurrences. On-treatment occurrences in the double-blind phase will be defined as occurrences in the period between the first dose of blinded study drug to the minimum of the last dose date of blinded study drug + 3 days and first dose date of open-label study drug, if applicable, for those who discontinued blinded study drug permanently. Off-treatment occurrences will be defined as occurrences after the last dose of study drug + 3 days. A supportive listing will also be generated.

Incidence of ALT flare and exacerbation of hepatitis is defined as:

- Serum ALT $> 2 \times$ study baseline and $> 10 \times$ ULN, with or without associated symptoms

OR

- Confirmed ALT elevation (defined as 1 grade shift [ie, increase] or $2 \times$ previous value) with confirmed changes outside of the normal range in other laboratory parameters suggestive of worsening hepatic function (abnormal prothrombin time ≥ 2 seconds over study baseline or international normalized ratio [INR] ≥ 0.5 over study baseline, and abnormal serum albumin ≥ 1 g/dL below study baseline or elevated serum lactate levels [if available], defined as $2 \times$ ULN).

If the first of two consecutive results is in the double-blind phase and the second is out of the double-blind phase (ie, in the open-label or TFFU phase), then the result will be considered to be confirmed in the double-blind phase (assuming both values meet the criterion). And if the criterion is met by the last value in the double-blind phase, and no assessments are available after due to the subject exiting the study or data not yet available (eg, due to the data-cut), then the result will also be considered to be confirmed.

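### SAP 3.8.1 and 3.8.2 class open-label TDF as treatment-free follow-up for any child who stops blinded drug early and then switches to it

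*SAP*

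**What the plan says.** **Routes to early open-label TDF.** Protocol Section 3 allows open-label TDF for a child whose Grade 4 ALT has lasted at least 16 weeks, and records the event as an adverse event leading to discontinuation of blinded drug. Protocol 5.1 stops study treatment when the code is disclosed to the investigator and then adds: "The subject can be offered open-label tenofovir DF after discussion with the Gilead Medical Monitor".

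**Last Dose Date (SAP 3.8.1).** There are two groups. The first is worded "For subjects who prematurely discontinued blinded study drug or who completed blinded study drug but did not enter the open-label phase", and its Last Dose Date is the last blinded dose. The second is worded "For subjects who completed blinded study drug and entered the open-label phase", and its Last Dose Date is the last open-label dose.

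**Phases (SAP 3.8.2).**
- For completers who enter open-label treatment, double-blind on-treatment time runs "up to and including the minimum of the Last Dose Date of Blinded Study Drug + 3 days and the Open-label Study Day 1".
- The other rule begins "If a subject prematurely discontinued blinded study drug or did not enter open-label phase after completion of blinded study drug". It runs to Last Dose Date + 3 days and does not mention Open-label Study Day 1.
- The open-label rule covers everyone given open-label drug and reads: "on-treatment assessments during the open-label phase will be defined as assessments that occurred during the period from Open-label Study Day 1". Its end point is Last Dose Date + 3 days.
- Treatment-free follow-up is everything after Last Dose Date + 3 days, up to the last study date.

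**ALT flares (SAP 7.2.3).** "Off-treatment occurrences will be defined as occurrences after the last dose of study drug + 3 days".

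**The concern.** A child who stops blinded drug early and then takes open-label TDF fits the first Last Dose Date group and not the second. That fixes Last Dose Date before open-label treatment starts, and three of the four phase rules the child needs (end of double-blind, end of open-label, start of follow-up) are tied to that date. Time on active drug is then labelled as time off treatment.

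This conflicts with Protocol Section 3, where off-treatment follow-up ends once active treatment begins. It also conflicts with the SAP's own rules for treatment-emergent adverse events (7.1.5.1) and laboratory abnormalities (7.2.2.1, 7.2.2.2). Those cut the double-blind phase at the earlier of blinded stop + 3 days and the first open-label dose, with no requirement that blinded drug was completed. The same child on the same day could be in the open-label phase for adverse events and in treatment-free follow-up for by-visit laboratory data.

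The outputs exposed are post-treatment laboratory data and their visit windows and, depending on programming, the off-treatment ALT flare summary. Children switched for sustained Grade 4 ALT are among those for whom a flare summary matters most.

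**Working it through.** The documents give no figure to reproduce, so the check applies the written rules to a hypothetical child.

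**Notation.** L is the day of the last blinded dose and S the day of the first open-label dose. Under the written rule Last Dose Date = L. Hence:
- double-blind on-treatment ends at L + 3, with no cap at S;
- open-label on-treatment runs from S to L + 3;
- treatment-free follow-up starts at L + 4.

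**Worked case (assumed days).** L = 196, S = 197, child still on open-label TDF at Day 336, the nominal Week 48 day in SAP Table 3-2.
- Open-label days to Day 336: 336 − 197 + 1 = 140.
- Counted as both double-blind and open-label: Days 197 to 199, 3 days. The completers' cap would leave only Day 197 shared.
- Counted as treatment-free follow-up: Days 200 to 336, 336 − 200 + 1 = 137.
- Day 336 is follow-up day 336 − 196 = 140, inside the Follow-Up Week 20 window (126 to 153, SAP Table 3-5).

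**Range over the assumed stop day.** With S = L + 1, open-label days to Day 336 are 336 − L, and those classed as follow-up are 333 − L.

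| L | Open-label days to Day 336 | Classed as follow-up | Window for the Day 336 visit |
|---|---|---|---|
| 28 | 308 | 305 | none (follow-up day 308 > 181) |
| 112 | 224 | 221 | none (follow-up day 224 > 181) |
| 196 | 140 | 137 | Follow-Up Week 20 |
| 280 | 56 | 53 | Follow-Up Week 8 |

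Day 112 is Week 16, about the earliest stop by the ALT route; the disclosure route has no minimum. If S is later than L + 3, the open-label interval ends before it begins and every open-label day is follow-up.

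**Alternative readings of 3.8.1.**
- If the condition about not entering the open-label phase is read as applying to both halves of the first group, these children have no Last Dose Date at all.
- If an analyst substitutes the last open-label dose against the written rule, the uncapped sentence in 3.8.2 makes all open-label time double-blind as well.

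**After the repair, same case.** Last Dose Date becomes the last open-label dose, and double-blind time ends at min(196 + 3, 197) = Day 197. All 140 days are then open-label on-treatment, one boundary day is shared (as for completers), and none is follow-up.

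**The case against.** **The primary endpoint.** A reader might infer that HBV DNA suppressed by open-label TDF could count as a placebo response at Week 48. The written rule does not allow that. Last Dose Date is the last blinded dose, so a value more than 3 days later is outside the double-blind phase. SAP Section 6 summarises efficacy for that phase only, and missing counts as failure (SAP 6.1.3; Protocol 8.6.1.1). The inference needs the substitution described above. Even then, assuming 60 and 29 treated children and response rates of 80% and 1%, five placebo switchers counted as responders raise the expected placebo rate to (5 + 24 × 0.01)/29 = 18.1% and leave Fisher power above 99.9%. This objection stands.

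**ALT flares.** SAP 7.2.3 refers to the last dose of study drug, not to the defined Last Dose Date, and 3.8.1 elsewhere spells out study drug as blinded or open-label. On plain words, a flare on open-label TDF is not off-treatment. This stands in part: misreporting is not certain, but nothing in 7.2.3 says which date to program.

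**Other safety rules.** Treatment-emergent adverse events, deaths and laboratory abnormalities do not use Last Dose Date and already handle these children. This stands.

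**Reach.** This SAP covers the Week 48 analysis. Summaries are mostly double-blind only, with later data in listings, so a reader who counts mislabelled exposure out to Week 192 goes beyond its planned output. This stands.

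**Disposition.** SAP 4.2 lists open-label entry only at Week 48 and Week 72 ("Entered open-label phase at Week 72"), which a reader might call a further error. Early stoppers are already counted, with reasons, as premature discontinuations of blinded drug. An extra row is a presentation preference.

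None of this supplies the missing rule in 3.8.1 and 3.8.2.

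**Conclusion.** The gap is real and narrow. As written, SAP 3.8.1 and 3.8.2 put nearly all open-label TDF time of an early switcher into treatment-free follow-up: 137 of 140 days to Day 336 in the worked case, and all but 3 days whenever open-label drug starts the day after the last blinded dose. Up to 3 days on TDF can also count as double-blind. This disagrees with Protocol Section 3 and with SAP 7.1.5.1, 7.2.2.1 and 7.2.2.2.

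The consequences are mislabelled post-treatment laboratory data and, only if 7.2.3 is tied to Last Dose Date, on-TDF flares reported as off-treatment exacerbations. The primary endpoint and the treatment-emergent safety tables are not affected under the written rules. The stop days are assumptions. The documents do not say how many children switched early, and the number may be zero. The point is worth correcting because a stated rule gives a wrong classification, not because a main conclusion is at risk.

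**What to change.** Four changes, all to analysis definitions:

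1. SAP 3.8.1: for every subject who took open-label drug, whether or not blinded drug was completed, define Last Dose Date as the last open-label dose. For all others it stays the last blinded dose.
2. SAP 3.8.2: for every subject who took open-label drug, end double-blind on-treatment time at the earlier of Last Dose Date of Blinded Study Drug + 3 days and Open-label Study Day 1.
3. SAP 3.8.2: start treatment-free follow-up only after the last dose of any study drug, blinded or open-label, + 3 days. It should not be worded as the last TDF dose, because a placebo child who never switched has none.
4. SAP 7.2.3: use that same Last Dose Date for off-treatment occurrences.

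Changes 1 and 2 must be made together. Changing Last Dose Date without the cap would turn all open-label time of these children into double-blind time and expose the primary endpoint.

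The cost is a few sentences and one revised derivation. No new data are needed, and the treatment rules in the protocol are untouched. The change should be made before the SAP is finalised; otherwise it should be documented in the clinical study report.

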3.8.2. Analysis Windows

Subject visits might not occur on protocol specified days. Therefore, for the purpose of analysis, observations will be assigned to analysis windows.

The following windows ([Table 3-2](#) to [Table 3-4](#)) apply to baseline and on-treatment assessments only; ie, data collected during the double-blind phase and open-label phase. For summaries and analyses, assessments will first be categorized into on-treatment assessments occurring during the double-blind or open-label phase, before applying analysis windows.

For subjects who completed blinded study drug and entered the open-label phase, laboratory and DXA assessments that occurred during the period from the first dose date of blinded study drug up to and including the minimum of the Last Dose Date of Blinded Study Drug + 3 days and the Open-label Study Day 1, will be considered as on-treatment during the double-blind phase. If a subject prematurely discontinued blinded study drug or did not enter open-label phase after completion of blinded study drug, then on-treatment assessments during the double-blind phase will be defined as assessments that occurred during the period from the first dose date of blinded study drug to the Last Dose Date + 3 days.

For subjects who entered the open-label phase, on-treatment assessments during the open-label phase will be defined as assessments that occurred during the period from Open-label Study Day 1 up to the Last Dose Date + 3 days.

Off-treatment assessments during the treatment free follow-up (TFFU) phase will be defined as assessments that occurred during the period after the Last Dose Date + 3 days up to the Last Study Date. Assessments during this period are considered post-treatment.

The analysis windows for HBV DNA, hematology, serum chemistry and liver tests, urinalysis, urine pregnancy test, height, weight, and vital sign assessments are presented in [Table 3-2](#).

Table 3-2. Analysis Windows for HBV DNA, Hematology, Serum Chemistry and Liver Tests, Urinalysis, Urine Pregnancy Test, Height, Weight, and Vital Sign Assessments

Visit ID	Nominal Day	Lower Limit	Upper Limit
Baseline			1
Week 4	28	2	41
Week 8	56	42	83
Week 16	112	84	139
Week 24	168	140	195
Week 32	224	196	251
Week 40	280	252	307
Week 48	336	308	363
Week 56	392	364	419
Week 64	448	420	475
Week 72	504	476	531
Week 80	560	532	587
Week 88	616	588	643
Week 96	672	644	713
Week 108	756	714	797
Week 120	840	798	881
Week 132	924	882	965
Week 144	1008	966	1049
Week 156	1092	1050	1133
Week 168	1176	1134	1217
Week 180	1260	1218	1301
Week 192	1344	1302	1385

The analysis windows for spine and whole body bone mineral density (BMD) results from DXA and bone biochemical markers: urine bicarbonate, urine n-telepeptide, serum c-telopeptides, osteocalcin, bone-specific alkaline phosphatase, serum parathyroid hormone (PTH), vitamin D levels (25-hydroxy) and (1,25-dihydroxyvitamin), fasting serum creatinine and fasting phosphate, urine creatinine (spot) and phosphate, and renal phosphate threshold (tubular maximum reabsorption rate of phosphate [TmP]/glomerular filtration rate [GFR]), are presented in [Table 3-3](#).

Table 3-3. Analysis Windows for Spine and Whole Body From DXA and Bone Biochemical Markers

Visit ID	Nominal Day	Lower Limit	Upper Limit
Baseline			1
Week 24	168	2	251
Week 48	336	252	419
Week 72	504	420	587
Week 96	672	588	839
Week 144	1008	840	1175
Week 192	1344	1176	1511

The analysis windows for HBV serology and quantitative HBsAg (qHBsAg) are presented in [Table 3-4](#).

Table 3-4. Analysis Windows for HBV Serology and qHBsAg

Visit ID	Nominal Day	Lower Limit	Upper Limit
Baseline			1
Week 16	112	2	167
Week 32	224	168	279
Week 48	336	280	391
Week 64	448	392	475
Week 72	504	476	531
Week 80	560	532	615
Week 96	672	616	713
Week 108	756	714	797
Week 120	840	798	881
Week 132	924	882	965
Week 144	1008	966	1049
Week 156	1092	1050	1133
Week 168	1176	1134	1217
Week 180	1260	1218	1301
Week 192	1344	1302	1385

Data collected after the TFFU phase will be considered as post-treatment visits. The analysis windows for post-treatment assessments are presented in [Table 3-5](#).

Table 3-5. Analysis Windows for Post-Treatment Assessments Except HBV Serology

Visit ID	Nominal Follow-Up Day	Lower Limit	Upper Limit
Follow-Up Baseline			4
Follow-Up Week 4	28	5	41
Follow-Up Week 8	56	42	69
Follow-Up Week 12	84	70	97
Follow-Up Week 16	112	98	125
Follow-Up Week 20	140	126	153
Follow-Up Week 24	168	154	181

Table 3-6. Analysis Windows for Post-Treatment HBV Serology and qHBsAg

Visit ID	Nominal Follow-Up Day	Lower Limit	Upper Limit
Follow-Up Baseline			4
Follow-Up Week 24	168	5	333

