6.2.2. Week 48 Assessments – End of Blinded Randomized Treatment

Study Visit for Week 48 should be completed ± 4 days of the protocol-specified visit date, based on the Baseline Visit. The following assessments and procedures will be performed and recorded on CRFs:

- Complete physical examination including Tanner Staging and vital signs
- Body weight and height
- Blood samples for:
 - Hematology (CBC with differential and platelet count)
 - Serum chemistry and liver function tests, including albumin, alkaline phosphatase, AST, ALT, total bilirubin (reflex to direct [conjugated] bilirubin if total bilirubin $> 1.5 \times$ ULN), bicarbonate, BUN, calcium, chloride, CPK, creatinine (and calculated creatinine clearance), glucose, LDH, magnesium, phosphorus, potassium, sodium, uric acid, and amylase (reflex lipase testing if total amylase is $\geq 1.5 \times$ ULN)
 - Serum bone biochemical markers, including serum c-telopeptides, osteocalcin, bone-specific alkaline phosphatase, PTH, vitamin D levels (25-hydroxy), 1,25 (dihydroxyvitamin) D levels, and fasting creatinine and fasting phosphate
 - Hepatitis B serology (HBeAg and HBsAg; reflex HBeAb and HBsAb if Ag negative)
 - Plasma HBV DNA (PCR method)
 - Serum β -HCG pregnancy test (females of childbearing potential only)
 - Serum for resistance surveillance
 - Plasma for determination of tenofovir concentration
 - Serum and plasma for storage (for potential pharmacokinetic and/or virologic assays, including resistance surveillance, HBsAg and HBeAg quantification and compliance assessment)

- Urine samples for:
 - Urinalysis (protein, glucose, blood)
 - Urine bone biochemical markers, including urine bicarbonate, urine n-telopeptide, and spot urine creatinine and phosphate
- DEXA scan of spine and whole body (DEXA scans may be performed \pm 10 days from the Week 48 visit).
- Review of AEs and concomitant medications
- Retrieval of study medication and assessment of medication adherence
- Study drug dispensing (including multivitamin) and instructions on appropriate dosing and administration

After 48 weeks of blinded randomized treatment, each subject will switch to open-label tenofovir DF treatment for an additional 144 weeks. Subjects under Protocol Amendment 3 who are beyond Week 48 of blinded randomized treatment will switch to open-label tenofovir DF at the Week 72 visit and will continue on open-label treatment until Week 192.

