6.1.3. Analysis of the Primary Efficacy Endpoint

The primary efficacy analysis will be conducted after the last randomized subject reaches Week 48 or discontinues study drug prematurely. The M = F approach will be employed for all data up to Week 48 using the Full Analysis Set. In this approach, all missing data will be treated as not having achieved the primary endpoint.

The analysis will evaluate the difference between treatment arms in the proportion of subjects achieving the primary endpoint, using a two-sided stratified Cochran-Mantel-Haenszel (CMH) test controlling for age at baseline (<6 and ≥6 years) and region (North America/Europe and Asia).

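### A Week 48 sample taken before the first open-label dose but 4 or more days after the last blinded dose drops out of the double-blind phase and can be scored as a failure

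*SAP*

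**What the plan says.** SAP 3.8.2 first sorts assessments into phases and only then applies the visit windows. For a child who completes blinded drug and goes on to open-label drug, double-blind laboratory data run "up to and including the minimum of the Last Dose Date of Blinded Study Drug + 3 days and the Open-label Study Day 1". Open-label on-treatment data are "assessments that occurred during the period from Open-label Study Day 1 up to the Last Dose Date + 3 days". Off-treatment follow-up covers "assessments that occurred during the period after the Last Dose Date + 3 days up to the Last Study Date". For such a child, SAP 3.8.1 says the Last Dose Date "is the latest non-missing end date of open-label study drug", so follow-up cannot begin before open-label treatment ends. SAP 3.8.1 also works in calendar days: "Open-Label Study Day 1 is defined as the day when the first dose of the open-label study drug was taken".

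SAP section 6 limits the Week 48 efficacy summaries to the double-blind phase. For the primary endpoint, SAP 6.1.3 adds that "all missing data will be treated as not having achieved the primary endpoint". SAP 3.6.1 applies the same Missing = Failure rule to the secondary proportions, including HBeAg seroconversion.

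On visit timing, Protocol 6.2.2 says: "Study Visit for Week 48 should be completed ± 4 days of the protocol-specified visit date, based on the Baseline Visit". The visit is tied to Baseline, not to the last blinded dose. Blood sampling and dispensing of the next study drug are both listed for this visit.

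**The concern.** The cut-off has two limbs. The Open-label Study Day 1 limb does what one would want: it keeps everything up to the switch and removes what comes after it. The + 3 days limb can override it. When it does, a result obtained before any open-label exposure is removed from the randomized comparison. The open-label phase has not yet started, or starts that day, so nothing returns the value to Week 48.

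The affected assessments carry the primary endpoint (HBV DNA), the key secondary endpoint (HBeAg seroconversion) and the ALT endpoints. A measured result would be replaced by an imputed failure. For HBV DNA the loss falls almost wholly on TDF, because placebo response is assumed to be 1%. For seroconversion and ALT, placebo children can also respond, so the direction is less one-sided.

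The rule also sits awkwardly with its own rationale. SAP 7.11 explains that 3 days were added because laboratory samples taken shortly after stopping drug were being lost although the visit windows allowed them. The margin chosen is 3 days, while the Week 48 visit may be 4 days late.

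**Working it through.** **Inputs.** The phase rules are from SAP 3.8.1 and 3.8.2. The Week 48 windows are Days 308 to 363 for HBV DNA and ALT (Table 3-2) and Days 280 to 391 for serology (Table 3-4). The visit tolerance is ± 4 days (Protocol 6.2.1 and 6.2.2). There are 89 treated children (SAP 1.3).

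**Step 1: classify by date.** Let S be the sample day, L the last blinded dose and O the first open-label dose.

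- Double-blind if S ≤ min(L + 3, O).
- Open-label if O ≤ S ≤ last open-label dose + 3.
- Follow-up if S > last open-label dose + 3.

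| S | L | O | min(L + 3, O) | Phase |
|---|---|---|---|---|
| 336 | 336 | 337 | 337 | double-blind |
| 336 | 333 | 337 | 336 | double-blind |
| 336 | 336 | 336 | 336 | meets both definitions |
| 336 | 332 | 336 | 335 | open-label only |
| 336 | 332 | 337 | 335 | none |
| 340 | 335 | 341 | 338 | none |
| 338 | 336 | 337 | 337 | open-label (true post-switch sample) |

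Rows 4 to 6 are the problem cases, where S is at least L + 4 and no later than O. A no-phase sample can still serve as the open-label baseline (SAP 3.8.1), but not as a Week 48 result.

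**Step 2: can an earlier scheduled sample stand in?** The Week 40 visit, about Day 280 ± 4, is outside Days 308 to 363. The Week 32 serology, about Day 224 ± 4, is outside Days 280 to 391. Normally nothing substitutes, although an unscheduled double-blind sample could.

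**Step 3: can a child within the visit window be affected?** If blinded dosing were exactly 336 daily doses, the last would fall on Day 336 and the cut-off on Day 339. With first dose on the Baseline day, nominal Week 48 is Day 1 + 336 = Day 337, and + 4 days gives Day 341. Samples on Days 340 and 341 are then lost. If the first dose is one day after Baseline, nominal is Day 336 and only Day 340 is lost. The condition that dosing stops on Day 336 is an assumption.

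**Step 4: do the other planned analyses recover the value?** No. Missing = Excluded (SAP 6.1.4) takes the child out of numerator and denominator. The Per Protocol set (SAP 3.1.4, Table 3-1) excludes a child without on-treatment Week 48 HBV DNA unless drug was stopped for lack of efficacy.

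**Step 5: size.** Arm sizes among the treated are not given. At 2:1, 89 × 2/3 = 59.3, so take about 60 on TDF and 29 on placebo. One lost responder costs 1/60 = 1.7 percentage points. As an illustration, start from 48/60 (80%, the revised assumption in SAP 1.3) against 0/29:

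| TDF responders rescored | TDF rate | Fisher p |
|---|---|---|
| 0 | 80.0% | 3.5 × 10⁻¹⁴ |
| 1 | 78.3% | 1.1 × 10⁻¹³ |
| 3 | 75.0% | 1.0 × 10⁻¹² |
| 6 | 70.0% | 3.2 × 10⁻¹¹ |

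Fisher's test is the planned supporting test; the stratified CMH was not computed.

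**The case against.** **The protocol does not create the gap.** This is the strongest reply. Protocol 6.2.2 presents Week 48 as the end of blinded treatment, medication is collected and dispensed at the visit, and SAP 1.2 describes a 192-week treatment period. Nothing tells a child to stop on Day 336 and wait for a late visit. If dosing runs to the visit, the last blinded dose is that day or the day before, well inside 3 days. This stands. A reader might infer that any child seen on Day 340 or 341 is lost, and the documents do not support that. It takes a dosing gap, from an interruption, from supply or from stopping at 48 weeks.

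**Supply is a weak route.** Bottles per visit are not stated. If 60 tablets were given at Week 40, a loss would need a Week 40 to Week 48 interval of 63 or 64 days, which is 3 of the 81 combinations of visit days allowed by ± 4 at each visit. This also stands.

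**The 3-day margin is deliberate.** It matches the 72-hour early discontinuation visit. That supports it for children who stop early. Completers who switch have no 72-hour requirement.

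**Harm is limited.** All efficacy data up to the data cut are listed, Missing = Excluded is planned, and the HBV DNA bias is against TDF. All true, but no planned summary uses the measured result.

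**Widening the phase has its own problem.** Without a limit, a child long off blinded drug could count as double-blind. The windows cap this: with a last dose on Day 336, at most 363 − 336 = 27 days for HBV DNA and 391 − 336 = 55 days for serology. Those caps are loose, so a flag is needed.

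**Conclusion.** The defect is real and narrow. As written, the rule removes valid pre-switch Week 48 results from the double-blind phase when the last blinded dose was 4 or more days earlier, and Missing = Failure turns them into failures unless another double-blind sample lies in the window.

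Three stronger readings are not supported:

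- Not every such sample is classed as open-label. That holds only for one drawn on Open-label Study Day 1; earlier ones belong to no phase.
- No rate of affected children can be derived. Children who stayed blinded to Week 72 are not exposed at Week 48, and SAP 6.1.5 calls the groups for which it withholds p-values small, including the one that reached Week 48 after Amendment 3. The number is probably small.
- The primary conclusion is not at risk. Even six rescored responders leave p below 10⁻¹⁰ in the illustration.

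What remains is about 1.7 points off the TDF rate per lost responder (assuming about 60 on TDF), a possible loss of key secondary events, for which the plan gives no planning rate, and some distortion of the comparison of children before and after Amendment 3, because only Week 48 switchers are exposed at that timepoint. The same rule applies to children switching at Week 72, where the visit tolerance is ± 6 days (Protocol 6.2.3) and Group 1 p-values are planned. This should be corrected, but it does not undermine the trial.

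**What to change.** In SAP 3.8.2, for children who complete blinded drug and enter open-label:

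- Count laboratory efficacy samples collected before the first open-label dose as double-blind, subject to the existing Week 48 (or Week 72) analysis windows. Where clock times are missing, treat a sample on Open-label Study Day 1 as pre-dose, as the present inclusive limit already does.
- Start open-label on-treatment data after the first open-label dose. This also removes the same-day overlap. The pre-dose sample remains the open-label baseline.
- Flag samples taken more than 3 days after the last blinded dose, and report their number by arm.
- State that the Per Protocol set in SAP 3.1.4 uses the same definition.

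Keep the + 3 days rule for children who stop early or do not enter open-label, and for the adverse event, laboratory abnormality and ALT flare definitions in SAP section 7.

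The cost is a short SAP edit and a programming change, to be made before unblinding. A few samples taken more than 3 days off drug will count as double-blind, and the efficacy and safety phase limits will differ slightly. A completer who does not enter open-label would still be held to 3 days, so handling depends on that choice; the flag lets a reader see how much this matters.
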